# PROTOCOL

### Background

#### 1. Provide the scientific background, rationale and relevance of this project.

There are many surgical wound closure methods commonly used in orthopaedic surgical practice today. These usually involve a combination of braided and monofilament sutures in the subcutaneous fascia and fat as well as the subcuticular layers of the skin. The methods chosen by surgeons vary widely even amongst partners at the same institution for many reasons, including training background and conflicting reports in the literature about optimal techniques. In some cases, these closure techniques can be time consuming and associated with increased rates of poor cosmetic outcomes or complications. Wound management has also become an increasingly important factor in patient satisfaction. There have been new wound closure products to reach the market (Zipline - Campbell, CA and Clozex - Wellesley, MA), claiming to increase the speed of closure, improve patient satisfaction and decrease the rate of complications. These products are FDA approved and both utilize an adhesive backed film to adhere to the skin along with a proprietary mechanism to promote skin apposition and reduce tension during the healing process. They have been shown to be safe and effective treatment options and have been adopted in many practices.

Our study aims to compare a traditional wound closure using both braided and monofilament sutures to the newer wound closure systems. By determining which method provides superior results, we will improve patient outcomes and satisfaction. The study also aims to assess health care value by exploring the costs associated with each closure technique. In addition to material expenses associated with the traditional sutures, we seek to explore if there is a significant difference in the time required to perform each wound closure method. Every minute of anesthesia and operating room utilization is associated with costs borne by the patient and the health care system. By finding which closure method is the fastest and associated with the best outcome we can improve healthcare value.

Our primary objective outcome measure will be an assessment of surgical scar characteristics using the Stony Brook Scar Evaluation Scale (SBSES) which has been validated in the assessment of surgical scars in the first year after surgery. Secondary outcome measures will include adverse events related to the surgical wound, surgical time for closure, a patient satisfaction score and physician satisfaction score.

# **Objectives/Hypothesis**

The objective of this study is to compare commonly performed wound closure methods in patients undergoing orthopaedic surgical procedures. The primary outcome measure is SBSES score. Secondary outcome measures include wound adverse events, surgical time, patient satisfaction scores, surgeon satisfaction scores and to determine any difference in the costs associated with each of the wound closure techniques. Our null hypothesis is that there will be no significant difference in terms of wound complication rates, patient satisfaction and surgeon satisfaction scores.

### **Study Design: Biomedical**

#### 1. Will controls be used? YES

Version Date: 07-29-22 Page Number: 1 of 8

#### ► IF YES, explain the kind of controls to be used.

The control will include an all-suture based wound closure consisting of braided Vicryl suture in deep fascia/fatty layers followed by monofilament 3-0 Monocryl subcutaneous suture and running 3-0 prolene subcuticular suture.

#### 2. What is the study design?

Randomized control study

3. Does the study involve a placebo?

### **Human Participants**

Ages: 18+ Sex: Male and Female Race: All

### Subjects

#### 1. Provide target # of subjects (at all sites) needed to complete protocol.

Surgical subjects: 30 Clinicians: 10

2. Describe expected rate of screen failure/ dropouts/withdrawals from all sites.

Surgical subjects: About 36% Clinicians: 0

### 3. How many subjects will be enrolled at all sites?

Surgical subjects: 83 Clinicians: 10

### 4. How many subjects will sign a consent form under this UVa protocol?

Surgical subjects: 83 Clinicians: 10

### **Inclusion/Exclusion Criteria**

### 1. List the criteria for inclusion

Surgical Subjects:

- Age 18+
- Patient scheduled to undergo elective orthopaedic surgical procedure with a minimum anticipated incision length of 3 cm.
- Willingness and ability to comply with scheduled visits and study procedures.

Clinicians:

Version Date: 07-29-22 Page Number: 2 of 8

- Attending surgeons, physician assistants and trainees (fellows and residents) in the orthopaedic surgery department
- Willingness to comply with randomization and study protocols

# 2. List the criteria for exclusion

Surgical subjects:

- Revision Surgery
- Compromised wound healing (autoimmune disorder, chronic steroids )
- Pregnant women, fetuses, neonates, children, prisoners, cognitively impaired, educational or economically disadvantage, non-English speaking subjects.
- Currently taking Immune modulating (DMARD) medications will exclude patient from participation in study
- Currently taking Chronic Steroids

Clinicians:

- None
- 3. List any restrictions on use of other drugs or treatments.

# **Statistical Considerations**

# **1.** Is stratification/randomization involved? YES

# ► IF YES, describe the stratification/ randomization scheme.

Simple randomization will be used. A random number generator will be used to devise a list to assign study numbers to treatment groups, ensuring that there will be equal numbers assigned to each group. No other variables will be used for stratification. For each study number, the treatment assignment will be placed into an envelope by the clinical trials coordinator and sealed.

There will be no blinding of subjects or personnel involved in the study once the envelope with group assignment has been opened.

The statistician doing the randomization and the clinical trial coordinator will be the only ones with access to the master treatment assignment list.

# ► IF YES, who will generate the randomization scheme?

Sponsor
X\_\_\_\_\_UVa Statistician: [name]
UVa Investigational Drug Service (IDS)
Other:

# 2. What are the statistical considerations for the protocol?

Primary outcome variable: SBSES scores will be assessed at scheduled post operative visits. The minimal clinically important difference will be defined as 1 point. The null hypothesis is that

there will be no difference between the SBSES scores between treatment groups (one-way ANOVA).

Secondary outcome variables: patient satisfaction with appearance of scar (on scale of 1-10), physician satisfaction with the technique/device (on a scale of 1-10), and presence or absence of adverse events (including infection and reoperation). For the scaled scores, descriptive statistics will be calculated, and means between groups will be compared (one-way ANOVA). A count of the adverse events per group will be tallied.

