# 5. What is your plan for secondary variable analysis?

Secondary outcome variables: patient satisfaction with appearance of scar (on scale of 1-10), physician satisfaction with the technique/device (on a scale of 1-10), and presence or absence of adverse events (including infection and reoperation). For the scaled scores, descriptive statistics will be calculated, and means between groups will be compared (one-way ANOVA). A count of the adverse events per group will be tallied.

Cost analysis between approaches will be assessed using the following metrics: the cost of operating room time per minute will be multiplied by the time for closure and added to the cost of materials to determine a total cost for each approach. The average costs for each approach will be compared using a one-way ANOVA to determine if there are significant differences in costs.

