# 7. Will data from multiple sites be combined during analysis? NO

# **Study Procedures-Biomedical Research**

### 1. What will be done in this protocol?

Patients who meet above inclusion criteria and provide informed consent will be enrolled in the study. All members of the research team that will be assisting with the surgical closure (including attending surgeons, fellows, residents and/or physician assistants) will receive full training in the application of both the Clozex and Zipline devices to insure uniform experience among participants. The clinicians performing the closure are also investigators in this research and may opt out of participating in this study. There are no pre-operative study procedures for the patients, aside from a review of inclusion and exclusion criteria and enrollment.

On the day of surgery, the enrolled subject will be randomized into one of three study groups. The randomization will occur during surgery, prior to wound closure. The circulating nurse will open an envelope, which will determine the randomization group for the subject. This will allow operating room staff the time to assemble the appropriate materials for closure depending on participant's group assignment without any delay to standard of care. The subjects' randomization into a treatment group is not expected to significantly increase the time of the operation or duration of anesthesia. The wound closure will proceed as follows:

- 1. Any deep fascial layers will be closed with braided Vicryl suture as indicated and according to standard of care.
- 2. The subcutaneous fat will be closed using 3-0 Monocryl in inverted, interrupted fashion according to standard of care.
- 3. The circulator will then start a timer that will run until the wound is completely closed.
  - A. If randomized to the **Control group**: Closure will proceed with a running 3-0 Prolene subcuticular suture with escape stitches.
  - B. If randomized to the **Clozex treatment group**: Closure will proceed with application of the adhesive device according to manufacturer's recommendations
  - C. If randomized to the **Zipline treatment group**: Closure will proceed with application of the adhesive device according to manufacturer's recommendations

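### Wound complication rates are named in a null hypothesis, but the plan gives them only a tally of events, with no denominator, interval or group comparison

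*Combined protocol and SAP*

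**What the plan says.** Under Objectives/Hypothesis, the protocol writes: "Our null hypothesis is that there will be no significant difference in terms of wound complication rates, patient satisfaction and surgeon satisfaction scores". The same section lists wound adverse events first among the secondary outcome measures.

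Statistical Considerations, item 2, describes the adverse-event variable as "presence or absence of adverse events (including infection and reoperation"), a yes/no status. Item 5 repeats this. On analysis, both items treat the satisfaction scores in one way: "For the scaled scores, descriptive statistics will be calculated, and means between groups will be compared (one-way ANOVA"). They treat adverse events in another: "A count of the adverse events per group will be tallied". Item 5 adds an ANOVA for cost and nothing further for adverse events.

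Study Procedures, item 1, has the clinician at follow-up record whether adverse events have occurred, at 14 to 17 days and again at 10 to 14 weeks. It also lets the provider switch to suture if a device fails, with the cross-over recorded. Subjects, item 2, expects about 36% screen failures, dropouts and withdrawals combined.

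**The concern.** A null hypothesis about rates calls for a rate in each group and some comparison between groups. A tally supplies neither. Three things are left open:

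- **The unit.** The variable is defined per subject, but the plan counts events.
- **The denominator.** The plan does not say whether it is all randomized subjects, those seen at a given visit, or those analysed for the scar score. It also does not say whether subjects who crossed over to suture stay in their assigned group.
- **The uncertainty.** With no interval, a reader cannot tell a low rate from too few patients.

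The background section cites claims that the devices lower complication rates, so readers will look for this result. Small counts shown without intervals could be taken as reassurance that the data cannot give.

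**Working it through.** **1. The parts of the hypothesis beside their planned analyses**

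| Part of the null hypothesis | Planned analysis (Statistical Considerations, items 2 and 5) |
|---|---|
| Patient satisfaction | Descriptive statistics, one-way ANOVA |
| Surgeon satisfaction | Descriptive statistics, one-way ANOVA |
| Wound complication rates | Count of events per group |

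No other section supplies a proportion, difference, interval or test for complications. Study Procedures, item 1, covers only how they are recorded.

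**2. Subjects or events**

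Take 10 analysed subjects in a group, one of whom has an infection at the first visit and a reoperation by the second. Counting subjects gives 1/10 = 10%. Counting events gives 2 per 10 subjects. At this size the choice alone doubles the figure.

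**3. The plan's own sample-size figure**

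The plan gives no sample size or expected rate for complications. Its 10 per group is for a 1-point scar-score difference with SD 0.73, alpha 0.05 and power 0.80. A two-group calculation reproduces 10. A three-group ANOVA with the third mean midway between the extremes gives 12, with 73.9% power at 10. Neither says anything about complications, so 10 and 20 per group (analysed and maximum enrolled, Statistical Considerations, item 3) serve below only as group sizes.

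**4. What zero events would show**

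The exact (Clopper-Pearson) two-sided 95% upper limit for 0/n is 1 − 0.025^(1/n):

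- n = 10: 1 − 0.025^(1/10) = 1 − 0.6915 = 30.8%
- n = 20: 1 − 0.025^(1/20) = 1 − 0.8316 = 16.8%

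If all 83 enrolled subjects were randomized and followed, 83/3 gives about 27 per group, and the limit would be 12.8%.

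**5. What a test could show, under assumed rates**

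The rates here are assumptions. Power is by full enumeration at alpha 0.05.

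| Per group | Pairwise Fisher, 5% vs 30% | Exact three-group test, 5%, 5%, 30% |
|---|---|---|
| 10 | 9% | 20% |
| 20 | 45% | 57% |

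At 10 per group the three-group test has 5% power for 5%, 20%, 20%; 6% for 5%, 5%, 20%; and 27% for 10%, 10%, 40%.

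**6. How often no events would be seen**

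At an assumed true rate of 10%, one group of 10 has no events with probability 0.9^10 = 34.9%. All three groups have none with probability 0.9^30 = 4.2%.

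**The case against.** The best defence is that describing rare events without a test is reasonable in a trial sized on a scar score. That stands: a test would have low power under most plausible assumptions, and none is demanded here. But a good description still needs a unit, a denominator and an interval, and a purely descriptive plan does not match a stated null hypothesis. It is also fair that the Objectives sentence is loosely drafted: it omits the scar score, whose own null hypothesis appears in Statistical Considerations, item 2. Deleting complication rates from the sentence would remove the mismatch, but would leave the unit and denominator unsettled.

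A reader might infer several stronger things that the documents do not support:

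- **That the groups will differ in size and follow-up.** The allocation plan speaks of "ensuring that there will be equal numbers assigned to each group", and all groups have the same two visits. Uneven loss is possible but is an assumption. The 36% also includes screen failures, some of which may come before randomization.
- **That the trial can neither test nor bound complication rates.** Each subject's status is recorded and group sizes will be known, so proportions and intervals can be computed. What is missing is their prespecification.
- **That a result of no events in any group is likely.** At a 10% rate and 10 per group, the 35% chance is for one group; for all three it is 4%.
- **That the plan intends to declare equal safety.** It states a null hypothesis and nowhere says that failure to reject it will be read as equality.

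**Conclusion.** The point holds as a mismatch between a stated hypothesis and its planned analysis, together with an unclear counting unit and no denominator. This part rests on the text and needs no assumption. The upper limits of 31% for 0/10 and 17% for 0/20 depend only on the group sizes and show why intervals matter. The documents give no complication rate, so every power figure depends on the assumed rates and on the group size reached. The 9% at 10 per group should not be quoted without the 45% at 20.

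The severity is low. Only a secondary outcome is affected, the primary analysis is untouched, and the gap can be closed before analysis without new data.

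**What to change.** In Statistical Considerations, items 2 and 5, replace the tally with the number and percentage (n/N) of subjects having at least one wound adverse event by the final visit, by assigned group, with cross-overs kept in that group. State who is in N and show how many subjects were not assessed. Give an exact 95% confidence interval for each group, and each device-minus-control difference with a 95% confidence interval by a named method. Event counts by type can be listed beside this. An exact p-value is optional and should be labelled descriptive.

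Under Objectives/Hypothesis, take complication rates out of the null hypothesis and say that they will be estimated descriptively.

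The cost is a few lines of wording in three places and no extra data. The price is wide intervals and a weaker safety statement, which is what groups of this size can support.

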# 3. Provide a justification for the sample size used in this protocol.

Based on research from Agarwala and Vijayvargiya (2019), average SBSES is 4.4 (SD = 0.73) for a post-operative orthopaedic surgical incision. If we are using a one-way ANOVA, alpha = 0.05, and power = 0.80, we would have the following sample sizes required for each group based on various differences between groups.

| Difference in means between groups | Standard deviation | Sample size required (for each group) |
|------------------------------------|--------------------|---------------------------------------|
| 2                                  | 0.73               | 4                                     |
| 1.5                                | 0.73               | 6                                     |
| 1                                  | 0.73               | 10                                    |
| 0.5                                | 0.73               | 43                                    |

We will be enrolling up to 20 patients per group to ensure that we will have 10 patients for analysis in each group.

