- 4. If at any time, the surgical provider (attending surgeon, fellow, resident, PA) determines that the device in the test group has failed (i.e. adhesive failure, device breakage), s/he may elect to proceed with suture closure and study cross over shall be recorded.
- 5. At the conclusion of the wound closure, the timer will be stopped and the operative time will be recorded.

Version Date: 07-29-22 Page Number: 5 of 8

Dressings will then be applied in standard fashion including 4 x 4 gauze, webril wrap and ACE bandage and splinting as indicated. The team member who performed the wound closure (attending surgeon, fellow, resident or PA) will fill out the survey on satisfaction with the closure (scale 1 - 10) and note any complications or confounding factors (challenging incision pattern or application problems). The subject will be discharged with standard wound care instructions to keep the surgical dressing in place for 3 days and then to replace it with clean sterile dressings. The subjects will be cautioned not to submerge their wound underwater for at least 2 weeks following surgery, as per standard protocol.

Initial follow up will occur at a standard time interval within 14 - 17 days after surgery, at which point Prolene sutures will be cut and removed and Clozex/Zipline devices will be removed. An assessment of the wound will take place by the same attending surgeon who performed the procedure using the Stony Brook Scar Evaluation Scale (SBSES) using the below rubric (scale 0 - 5).

| Category                 |   | Points |
|--------------------------|---|--------|
| Width                    | > 2 mm  | 0      |
|                          | ≤ 2 mm  | 1      |
| Height                   | Elevated/ depressed in relation to surrounding skin | 0      |
|                          | Flat  | 1      |
| Color                    | Darker than surrounding skin                        | 0      |
|                          | Same color or lighter than surrounding skin         | 1      |
| Hatch marks/Suture marks | Present   | 0      |
|                          | Absent  | 1      |
| Overall appearance       | Poor  | 0      |
|                          | Good  | 1      |
|                          |   |        |

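### From the plan's only planning mean (4.4 on a scale that ends at 5), the 1-point target can be met only as a worsening, so the 80% power does not cover a gain over that mean

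*Combined protocol and SAP*

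**What the plan says.** Under Statistical Considerations, item 3 (sample size), the planning input is "average SBSES is 4.4 (SD = 0.73"), given for an orthopaedic incision after surgery in general. The settings are "If we are using a one-way ANOVA, alpha = 0.05, and power = 0.80". A table gives the number per group for four differences at SD 0.73: 4 for 2 points, 6 for 1.5, 10 for 1 and 43 for 0.5. Up to 20 per group are enrolled so that 10 per group can be analysed.

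Item 2 explains the choice of row: "The minimal clinically important difference will be defined as 1 point". Its null hypothesis has no direction: "there will be no difference between the SBSES scores between treatment groups (one-way ANOVA").

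The Study Procedures section scores the scar at the 14-17 day visit "using the below rubric (scale 0 - 5"), as five items worth 0 or 1, and repeats the score at 10-14 weeks. Subjects go to a suture control, Clozex or Zipline: "the enrolled subject will be randomized into one of three study groups".

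The Background gives the purpose: "By determining which method provides superior results, we will improve patient outcomes and satisfaction".

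The plan does not mention the upper limit of the scale in connection with the sample size. It does not say which arm or visit the 4.4 describes, or in which direction the 1-point difference is expected.

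**The concern.** A planning mean of 4.4 leaves 0.6 of room below the maximum. A device that is 1 point better than 4.4 would need a mean of 5.4. The difference that fixes the sample size is therefore out of reach in the direction of benefit, unless the control mean is lower than the one mean the plan gives.

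The 80% figure is what a reader will rely on when interpreting the primary result. Someone who takes it as the chance of detecting a better device would overestimate what 10 per group can do, and would give a non-significant ANOVA more weight as evidence against a benefit than it can bear.

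**Working it through.** **Inputs.** Mean 4.4, SD 0.73, alpha 0.05, power 0.80, one-way ANOVA and 10 analysed per group (Statistical Considerations, item 3); target difference 1 point (item 2); three groups and maximum score 5 (Study Procedures, item 1).

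**1. The plan's own figure.** For a two-sample t test the noncentrality is d / (SD × √(2/n)). With d = 1 and n = 10 this is 1 / (0.73 × 0.447) = 3.06 on 18 df. Power is 82.5%, and 10 is the smallest n that reaches 80%. For a three-group ANOVA, λ = n × Σ(mean − grand mean)² / SD²:
- means (0, 0, 1): λ = 10 × 0.667 / 0.533 = 12.5, power 86%, n for 80% = 9;
- means (0, 0.5, 1): λ = 10 × 0.5 / 0.533 = 9.4, power 74%, n for 80% = 12.

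The stated 10 matches the t test exactly and lies between the two ANOVA answers.

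**2. Which rows are attainable as a gain over 4.4.** 4.4 + 2 = 6.4; 4.4 + 1.5 = 5.9; 4.4 + 1 = 5.4; 4.4 + 0.5 = 4.9. Only the last is on the scale, and its row asks for 43 per group. The largest gain is 5 − 4.4 = 0.6. A 1-point gain needs a control mean of at most 5 − 1 = 4.0. A 1-point fall, to 3.4, is possible; simulated with SD 0.73 it has about 83-84% power at 10 per group.

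**3. Constant-SD approximation at 0.6.** With n = 10:
- means (0, 0, 0.6): λ = 10 × 0.24 / 0.533 = 4.5, power 42%;
- means (0, 0.3, 0.6): λ = 10 × 0.18 / 0.533 = 3.4, power 32%.

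These figures cannot hold at the ceiling. A mean of 5 requires every score to be 5, so that arm's SD is 0, not 0.73.

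**4. Power on the bounded score.** Assumption: control scores of 3, 4 and 5 with probabilities 0.143, 0.314 and 0.543. The mean is 3 × 0.143 + 4 × 0.314 + 5 × 0.543 = 4.40 and the SD 0.725. Device distributions are the same shape tilted upward to the stated mean, so their SD shrinks. The results are simulated one-way ANOVA rejection rates at 0.05 with 10 per group.

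| Device mean | Gain | One device better | Both devices better |
|---|---|---|---|
| 4.7 | 0.3 | 14% | 16% |
| 4.8 | 0.4 | 23% | 30% |
| 4.9 | 0.5 | 39% | 54% |
| 5.0 (all score 5) | 0.6 | 63% | 84% |

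A second assumed shape, spread over the whole scale with mean 4.40 and SD 0.73, gives figures within about 2 percentage points of these.

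**5. More than 10 analysed.** At the plan's 36% loss, 20 per group leaves 20 × 0.64 = 12.8. The 83 enrolled would leave 83 × 0.64 / 3 = 17.7 per group. If all 20 were analysed, the same simulation gives 51% (one device) to 59% (both) at 4.8, and more than 99% if every device patient scores 5.

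**The case against.** The strongest reply is that nothing in the plan ties 4.4 to the suture arm. It is an average for a generic orthopaedic incision, and the control here is a specific subcuticular closure scored at two visits. If 4.4 were the average over the three groups, means of 3.9, 4.4 and 4.9 would differ by 1 point within the scale. This stands: a reader might infer that a 1-point benefit is impossible, and the documents support that only on the condition that 4.4 is the control mean. It does not clear the plan, because 4.4 is the only mean given and no lower control mean is assumed anywhere.

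Second, the null is non-directional, and a search for the superior method includes finding that sutures are better. This also stands. The plan nowhere claims 80% power for a device beating suture, and a reader who infers that the sample size was miscalculated would be wrong (step 1).

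Third, it is tempting to say that power is 32-42% at the largest possible gain. Step 3 shows why that cannot be used; at that gain the bounded score gives 63% to 84%. The low figures belong to smaller gains.

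Fourth, gains of up to 0.6 fall below the plan's own minimal important difference. At SD 0.73 the 95% interval for a device-control difference has half-width 2.052 × 0.73 × √(2/10) = 0.67, so an estimate near zero would exclude a 1-point difference. That is fair, and it is a reason to report the intervals. A reader might also infer that the sponsor intends to treat a null result as equivalence; no section says so.

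Finally, more than 10 per group may be analysed. Power would then be higher (step 5), but the plan justifies its size at 10.

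**Conclusion.** The point holds conditionally. If 4.4 is the control mean, the 1-point target can be met only as a worsening, and the 80% power does not extend to any gain a device could achieve, except in the extreme case where both devices score 5 in every patient (about 84%). For device means of 4.7 to 4.8, power at 10 analysed per group is about 14% to 30%. These percentages rest on an assumed score distribution, though two shapes give nearly the same results. The arithmetic of the ceiling needs no such assumption. The condition fails if the true control mean is 4.0 or lower at the visit that counts, which the plan does not state. Severity: should-fix. The sample size agrees with its stated inputs; what is missing is a statement of what the power covers.

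**What to change.** Keep the sample size, endpoint and test, and amend Statistical Considerations, items 2 and 3:

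- State the control mean assumed for the score and the visit (14-17 days or 10-14 weeks) to which it applies.
- State that, from a mean of 4.4, the 1-point target can be met only as a worsening and that the largest gain is 0.6. If a control mean of 4.0 or lower is expected, say so and give the basis.
- Restate power for attainable gains using the bounded score, as in the table above, with the assumed distribution shown. Omit the constant-SD 32-42%, or label it as an approximation that cannot hold at the ceiling. Power at more than 10 analysed per group may be added as a range.

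In item 4 (primary analysis), add each device-control difference with its 95% confidence interval alongside the ANOVA. State that a non-significant result will be judged from those intervals and not taken as evidence of no difference.

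The cost is wording and a short recalculation. No extra patients are needed; the stated power becomes less favourable.

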# 4. What is your plan for primary variable analysis?

Primary outcome variable: SBSES score. A one-way ANOVA will be employed to compare mean scar assessment scores between groups.

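### The sample-size table does not come from one calculation: the 1-point row prints 10 per group, but the three-mean pattern that reproduces the other rows needs 12

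*Combined protocol and SAP*

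**What the plan says.** The trial compares a control suture closure with two adhesive devices; "the enrolled subject will be randomized into one of three study groups" (Study Procedures, item 1). Allocation is equal (Statistical Considerations, item 1). For the primary outcome, the SBSES score, "A one-way ANOVA will be employed to compare mean scar assessment scores between groups" (item 4). Item 2 fixes the effect of interest: "The minimal clinically important difference will be defined as 1 point".

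Item 3 takes an SD of 0.73 from a cited study and continues: "If we are using a one-way ANOVA, alpha = 0.05, and power = 0.80, we would have the following sample sizes required". The table then gives, per group:

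| Difference | Printed n |
|---|---|
| 2 | 4 |
| 1.5 | 6 |
| 1 | 10 |
| 0.5 | 43 |

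The 1-point row is carried forward: "We will be enrolling up to 20 patients per group to ensure that we will have 10 patients for analysis in each group". Under Subjects, item 1, the total needed to complete the protocol is "Surgical subjects: 30 Clinicians: 10", that is, 3 × 10 surgical subjects. Item 2 gives the expected screen failure, dropout and withdrawal: "Surgical subjects: About 36% Clinicians: 0". Items 3 and 4 there give 83 surgical subjects enrolled and consented.

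**The concern.** With three groups, a single difference in means does not determine the power of a one-way ANOVA; the position of the third mean matters too. Item 3 does not give it. That omission would be harmless if some pattern reproduced the table, because a reader could then infer the assumption. None does. The row out of step with the simplest reading is also the row that sets the target.

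This table is the protocol's only sample-size justification. As it stands, a reader cannot tell whether 10 evaluable patients per group give the stated 80% power for the minimal clinically important difference.

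**Working it through.** **Inputs.** Three groups of equal size (Study Procedures, item 1; Statistical Considerations, item 1). Alpha 0.05, power 0.80 and SD 0.73 (Statistical Considerations, item 3). Assumptions added here: normal errors, a common SD, and the tabled difference D read as largest minus smallest mean.

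**Formula.** Put the means at 0, xD and D, with x between 0 and 1. The F statistic has 2 and 3(n − 1) degrees of freedom and noncentrality

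λ = n · c · (D/0.73)², with c = (2/3)(1 − x + x²).

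So c = 1/2 when the third mean is midway (x = 0.5) and c = 2/3 when two means are equal (x = 0). The required n is the smallest with power of at least 0.80.

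**Reproducing the table.** Third mean midway:

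| D | λ at the required n | Required n (power) | Printed n |
|---|---|---|---|
| 2 | 4 × 0.5 × 4/0.5329 = 15.01 | 4 (83.6%) | 4 |
| 1.5 | 6 × 0.5 × 2.25/0.5329 = 12.67 | 6 (82.7%) | 6 |
| 1 | 12 × 0.5 × 1/0.5329 = 11.26 | **12 (82.6%)** | **10** |
| 0.5 | 43 × 0.5 × 0.25/0.5329 = 10.09 | 43 (80.9%) | 43 |

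Three rows match exactly. In the 1-point row, n = 10 gives λ = 10 × 0.5/0.5329 = 9.38 and power 73.9%. Power is 78.6% at n = 11, still short, so rounding does not explain the 10.

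**Other bases.**

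| Basis | D = 2 | 1.5 | 1 | 0.5 |
|---|---|---|---|---|
| Printed | 4 | 6 | 10 | 43 |
| Three groups, third mean midway | 4 | 6 | 12 | 43 |
| Three groups, one differs from two equal | 4 | 5 | 9 | 32 |
| Three groups spaced D apart (0, D, 2D) | 3 | 3 | 4 | 12 |
| Two-group test | 4 | 5 | 10 | 35 |

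**Every position of the third mean.** Moving x from 0 to 0.5 (the other half is symmetric) takes the rows from 4/5/9/32, through 4/6/10/37 and 4/6/11/41, to 4/6/12/43. The set 4/6/10/43 never occurs. In terms of c:

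- a printed 43 in the 0.5 row needs c between 0.489 and 0.501, so the third mean lies at 46% to 54% of the range;
- a printed 10 in the 1-point row needs c between 0.575 and 0.648, so the third mean lies within about 16% of one end. The 0.5 row is then at most 37.

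The intervals do not overlap. They do not overlap for two groups (0.398–0.408 against 0.468–0.527) or four groups (0.553–0.567 against 0.648–0.730) either.

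**Power at 10 per group for a 1-point range.**

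| Position of third mean | Power |
|---|---|
| Midway | 73.9% |
| 0.2 from one end | 78.9% |
| 0.1 from one end | 82.2% |
| At one end | 85.8% |

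The range detectable with 80% power at 10 per group is 1.07 with the third mean midway and 0.93 if one group differs from two equal groups. Simulation with 200,000 trials gave 73.8% (midway, n = 10), 85.8% (one differs, n = 10) and 82.6% (midway, n = 12).

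**The case against.** The strongest reply is that the table does not show which row is wrong. A third mean at about 13% to 16% of the range gives 4, 6 and 10 exactly, with 36 or 37 in the last row. That also matches three rows of four, and it makes the 0.5 row, on which no target depends, the odd one out. A two-group test gives 10 in the 1-point row as well (power 82.5%). So 10 is not shown to be too few. This stands. Midway is the simpler convention and reproduces the other three rows, but it is an inference, because the plan states no pattern. The reply does not rescue the table: each basis that gives 10 contradicts the printed 43.

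A second reply is that enrolment covers the gap. With 36% loss, 20 per group leaves 20 × 0.64 = 12.8. If all 83 enrol, 83 × 0.64 ≈ 53 remain, about 17.7 per group, and power with the third mean midway is already 94.4% at 17 per group. This limits the practical effect, but the enrolment figures need reconciling: three groups of 20 make 60, not 83. Moreover 30/83 = 36.1%, so 36% might be the share retained rather than lost. On that reading 20 per group leaves 20 × 0.36 = 7.2. Whatever the yield, the stated evaluable target is still 10 per group, and its justification remains unsound.

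**Conclusion.** The concern holds. The printed rows cannot come from the single one-way ANOVA calculation that item 3 describes, whatever the position of the third mean. On the pattern that reproduces the other three rows, the 1-point row should read 12, and the evaluable total 36 instead of 30.

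The effect is modest: at most 2 patients per group and about 6 power points (73.9% against 80%), and only if the trial ends with exactly 10 per group and the third mean is near the middle. If two groups have nearly equal means, 10 per group is enough. The result rests on a common SD of 0.73, normal errors and the difference read as the range of the three means. It should be fixed because the affected row sets the target and the correction costs little.

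**What to change.** Choose one of these in Statistical Considerations, item 3:

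- **State one pattern of means and recompute all four rows from it.** If one group differs from two equal groups, the rows become 4, 5, 9 and 32, and 10 per group is sufficient.
- **Correct the 1-point row to 12.** State that the third mean is taken as midway, give the power as 82.6%, and set the evaluable target at 12 per group (36 under Subjects, item 1). With 36% loss this needs 12/0.64 = 18.75, so 19 enrolled per group, within the limit of 20. If 36% were the share retained, it would need 12/0.36 = 33.3, so 34 per group. Reconcile the 36%, the 83 and the 20 per group before adopting this option.
- **Keep 10 and report its power.** For a 1-point range it is about 74% with the third mean midway (80% for a range of about 1.07), rising to about 86% if only one group differs.

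The first and third options change only wording in item 3. The second also changes Subjects, item 1. The price is a less favourable stated power or a slightly larger evaluable target. The one-way ANOVA itself does not change.
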